8 SUBJECT TREATMENT

8.1 Treatment Regimen

Subjects will be assigned to one of five treatment arms and will receive a single injection of product. The total volume of product administered will be approximately 300 μ L.

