9.4 Monitoring and Recording of AEs and SAEs

9.4.1 Adverse Events

Any AE experienced by the subject from Visit 2 (Day 1) through Visit 10 (Month 12) is to be recorded in the eCRF, regardless of the severity of the event or its relationship to study treatment.

Any AEs already documented at a previous assessment and designated as ongoing, should be reviewed at subsequent visits as necessary. If these have resolved, this should be documented.

Changes in intensity or frequency of AEs should be recorded as separate events (i.e., a new record started).

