4.4 Trial Treatment

Subjects eligible to be treated will receive a single injection of AURN001 (*neltepedocel* with Y-27632), *neltepedocel* alone, or Y-27632 alone into the anterior chamber of the study eye. The dose of *neltepedocel* will be either 1.0×10^6 , 5.0×10^5 or 2.5×10^5 cells; the dose of Y-27632 will be 100 μ M. The total volume of administration will be approximately 300 μ L.

The injection of study treatment into the study eye will be performed under local anesthesia (administration method at the investigator's discretion). After creating a small incision at the corneal limbus, the corneal endothelium will be polished to a diameter of approximately 8 mm. Study treatment will be injected into the anterior chamber using a 27-gauge needle. Immediately after completion of surgery, subjects will lie face down for approximately 3 hours (± 15 minutes).

For detailed instructions, please refer to the Procedure Manual, which includes sponsor observation language.

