6.4 Definition of Study Day

Start day of study treatment is the day of the first dose of study treatment, i.e. Day 1 as defined in the protocol.

The study day for assessments occurring on or after the start of study treatment (e.g., adverse event onset) will be calculated as:

Study day = Date of the assessment/event - start date of study treatment + 1.

The study day for assessments occurring prior to the first dose of study treatment (e.g., medical history) will be negative and calculated as:

Study day = Date of the assessment/event - start date of study treatment.

The study day will be displayed in all relevant data listings.

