7.11 Partial or Missing Date Handling

Partial or missing dates will be imputed when complete dates are required to flag data as treatment-emergent or concomitant with treatment.

Partial/missing start and end dates for AEs and concomitant medications will be imputed as follows.

Partial/missing start date:

- Dates with missing day only will be imputed as the 1st of the month unless the month and year are same as the month and year of first dose of study medication, in which case missing day will be imputed as the first dose day of study medication.
- Dates with both day and month missing will be imputed as 1 Jan unless the year is same as the year of first dose of study medication, in which case missing day and month will be imputed as the first dose day and month of study medication.
- Completely missing dates will be imputed as the first dose date of study medication unless the end date is on or before the first dose date of study medication, in which case missing date will be imputed as 1 Jan of the same year as the end date.

Partial/missing end date:

- Dates with missing day only will be imputed as the last day of the month.
- Dates with both day and month missing will be imputed as 31 Dec.
- If the ongoing flag is missing or “Yes” then the date will not be imputed unless death date is available, in which case the missing date will be imputed as the death date. If ongoing is “No” then the missing end date will be imputed as the last dose date.
- If the imputed date is after the date of death, then the end date will be set equal to the date of death.
- The original dates will be displayed in data listings and the imputed dates will be used in derivations only (study day, treatment-emergence status, etc.).

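### The SAP's default for a missing end date is the last dose date, which is always Day 1 in this single-injection trial, so the rule can give impossible end dates and leave some flags undetermined (wrong as written, minor)

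*SAP*

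**What the plan says.** SAP 7.11 imputes dates for adverse events and concomitant medications where flags need them. Partial end dates go to the end of the month or to 31 December. For a completely missing end date the rule depends on the ongoing flag. If the record is marked not ongoing, "then the missing end date will be imputed as the last dose date".

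A completely missing start date becomes the first dose date, "unless the end date is on or before the first dose date of study medication"; in that case it becomes 1 January of the year of the end date.

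There is only one dose. Protocol 8.1 states: "Subjects will be assigned to one of five treatment arms and will receive a single injection of product". SAP 4.4 agrees ("Subjects eligible to be treated will receive a single injection of AURN001"), and SAP 6.4 fixes the date: "Start day of study treatment is the day of the first dose of study treatment, i.e. Day 1 as defined in the protocol". Follow-up is long by comparison. Protocol 9.4.1 states: "Any AE experienced by the subject from Visit 2 (Day 1) through Visit 10 (Month 12) is to be recorded".

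SAP 14.1 defines a treatment-emergent event by its onset, or its worsening, from the injection onward. SAP 11.2 counts a drug begun before Day 1 as concomitant only if its use carried on for some time after the Day 1 administration.

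**The concern.** The last dose date is a workable default when dosing continues through follow-up. Here the first and last dose are the same injection, so the default places the end of every such record on Day 1, even when the event or drug began months later.

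Day 1 is also the boundary for both flags that SAP 7.11 is meant to support. An end date placed on that boundary can trigger the 1 January exception for a missing start. It also leaves open whether a drug begun before Day 1 continued past the injection. What is at stake is the accuracy of the treatment-emergent adverse event tables, which serve the secondary (safety) objective, and of the concomitant medication tables.

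**Working it through.** The documents give no figure to reproduce on this point. The check applies the SAP 7.11 rules to each pattern of missing dates.

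**Inputs.** Last dose date = first dose date = Day 1 (Protocol 8.1; SAP 4.4 and 6.4). Adverse events are recorded from Day 1 to Month 12, nominally Day 360 (Protocol 9.4.1 and Appendix 1). Planned arm size is 20 (Protocol Table 1). The calendar year 2024 (366 days) is assumed for illustration.

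**(a) Start known, end completely missing, not ongoing.** Duration = end day - start day + 1, with end day = 1.
- Onset Day 30: 1 - 30 + 1 = -28 days.
- Onset Day 40: 1 - 40 + 1 = -38 days.
- Onset Day 180: 1 - 180 + 1 = -178 days.

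Over onset Days 1 to 360, the end precedes the start on 359 of 360 days, that is, on all but Day 1. Treatment-emergent status is lost on 0 of 360, because it depends on onset.

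**(b) Both dates completely missing, not ongoing.** The result depends on which date is imputed first.
- Start first: there is no end date to trigger the exception, so start = Day 1. Status is lost for 0 of 366 possible injection dates.
- End first: end = Day 1, which satisfies the exception, so start = 1 January. Status is lost for 365 of 366 injection dates (all but 1 January itself). With injection on 15 May 2024, the start falls 31 + 29 + 31 + 30 + 14 = 135 days before injection.

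SAP 7.11 lists the start rules first. It does not say that this is the order of execution, or that the end date in the exception must be a reported one.

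**(b2) Start completely missing, end reported as Day 1.** This case needs no assumption about order. Because the exception includes the first dose date itself, the start becomes 1 January and the event is not treatment-emergent (unless injection was on 1 January). Yet Protocol 9.4.1 has adverse events recorded only from Day 1. A brief event on the day of surgery would fit this pattern.

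**(c) Drug begun before Day 1 and stopped later on an unknown date, not ongoing.** Imputed end = Day 1. If SAP 11.2 requires use strictly after Day 1, the drug is not concomitant. If Day 1 counts, it is.

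**With a follow-up-based end date.** The end date was set to Day 360 for illustration, and onset Days 1, 2, 8, 30 and 180 were run with the start known and with it missing. No end preceded its start, and treatment-emergent status was kept under either order.

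**The case against.** The strongest reply is that little of this reaches a table. SAP 7.11 imputes only where a flag needs a complete date, and an event with a known onset on Day 40 needs no end date to be flagged. No analysis of event duration is planned, and listings show the original dates. Events are asked about at every visit, ongoing ones are reviewed, and data are cleaned before each report, so a resolved event with neither date known should be rare. A drug begun after Day 1 is concomitant by its start date alone.

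Most of this stands, and it limits the size of the problem. It does not make the rule correct. SAP 7.11 names study day among the uses of imputed dates, and SAP 6.4 displays study day in relevant listings, so an end on Day 1 could appear beside a later onset. The order of imputation remains unstated, and cases (b2) and (c) do not depend on it.

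A reader might infer that every resolved event with a missing end date leaves the treatment-emergent tables. The documents do not support that: a known onset is enough to keep the event in, and partial end dates follow other rules. A reader might also infer that the error always runs toward fewer events and fewer concomitant drugs. That is not shown either. A completely missing start normally defaults to Day 1, which favours treatment-emergence. If Day 1 counts under SAP 11.2, a drug actually stopped before surgery would be added.

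**Conclusion.** The default end date is wrong as written. It suits repeated dosing and gives an impossible date for any record that starts after Day 1. The expected effect is small, so the severity is minor.

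Loss of treatment-emergent status is conditional. It requires a completely missing start date together with either an imputed end date that is allowed to trigger the 1 January exception, or a reported end on Day 1. The concomitant flag is ambiguous only for drugs begun before Day 1 with an unknown stop date.

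The number of such records cannot be known from the documents and is probably small. With 20 subjects per arm, one subject dropped from a table row changes it by 1/20 = 5 percentage points, but only if the lost event was that subject's only one in the row. No efficacy analysis is affected. The conclusion assumes that the last dose date means the date of the single study injection; the documents offer no other reading.

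**What to change.** In SAP 7.11:

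1. Replace the last dose date with the date of the subject's last study visit or contact, never earlier than the start date of the record.
2. State that only a reported end date, not an imputed one, can trigger the 1 January exception. For adverse events, limit the exception to end dates strictly before the first dose date.

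The second change makes the order of imputation irrelevant to treatment-emergent status and closes the Day 1 case.

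The cost is about two sentences and a small programming change, best made before the unmasked Month 6 reporting. There is one small downside: a few drugs actually stopped before Day 1 on an unknown date will be counted as concomitant. The SAP can say so.

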7.12 Subpopulations

Not applicable.

8 SUBJECT DISPOSITION

Subject disposition will be summarized by treatment group and overall.

The disposition table will include the numbers of subjects

- who were screened, screened but not randomized, randomized, and randomized but not treated,
- in full analysis set, in per-protocol set, and in safety analysis set.
- discontinued the study prior to Month 6,
- discontinued the study and completed the study.

The percentages will be calculated using the number of subjects from the full analysis set as the denominator, unless otherwise noted. Reasons for study discontinuation will be summarized. Inclusion and exclusion criteria not met for screening failure subjects will also be summarized.

Subject disposition data will be presented in a listing.

9 PROTOCOL DEVIATIONS

Protocol deviation will be reviewed by the sponsor at on-going basis. The deviation file will include a description of the protocol deviations, as well as classification of major or minor. Major deviations will further be categorized by different deviation categories. Number and percentage of subjects with major protocol deviations will be summarized by deviation category. For the protocol deviation summaries, any data collected at and after rescue visits will not be used.

Protocol deviations, including both major and minor deviations, will be presented in a listing.

The final criteria for the per-protocol set, regarding which protocol deviations that warrant exclusion, will be determined during the blinded data review when all data on protocol deviations are available and before breaking the blind.

10 DEMOGRAPHIC AND BASELINE CHARACTERISTICS

10.1 Demographics

The demographic variables collected in this study include age, gender, ethnicity, and race.

Age (years) will be summarized using descriptive statistics as a continuous variable. Age group (< 65 years, \geq 65 years) gender, ethnicity, and race will be summarized using counts and percentages.

Demographic characteristics will be presented in a listing.

10.2 Baseline Characteristics

Baseline characteristics will be summarized for study eye and non-study eye separately.

The following baseline characteristics will be summarized:

- BCVA (ETDRS)

- Central corneal thickness (CCT)

■ [REDACTED]

■ [REDACTED]

The subject baseline characteristics will be presented in a listing.

In addition, screening BCVA will be summarized for study eye and non-study eye separately.

- Number of subjects with BCVA < 65 letters and \geq 65 letters

11 MEDICAL HISTORY AND MEDICATIONS

11.1 Medical History

Ocular and non-ocular medical history will be coded using Medical Dictionary for Regulatory Activities (MedDRA) version 26.1 and summarized by system organ class (SOC) and preferred term (PT). Subjects are counted only once under each SOC or PT for which they have at least one medical history.

Ocular medical history will be summarized using discrete summary statistics and presented separately for study eye and non-study eye. Non-ocular medical history will be similarly summarized but at the subject level.

Subject medical history data will be presented in separate listings for ocular and non-ocular data.

11.2 Prior and Concomitant Medications

Prior and concomitant medications will be coded using the World Health Organization Drug Dictionary (WHODRUG) GLOBAL B3 September 1, 2023 and summarized by therapeutic drug class (Anatomical Therapeutic Chemical [ATC] 3 classification) and preferred name. Subjects are counted only once under each therapeutic class or preferred name (generic drug name) for which they have at least one concomitant medication. If the ATC3 classification is not provided, then the next lowest classification that is provided in the coding dictionary will be used.

Concomitant medications are medications which started 1) prior to initiation of study treatment administration and continuing for any period of time following the Day 1 administration of study treatment or 2) at any time following the Day 1 administration of study treatment. Prior medications are medications which are started before the Day 1 administration of study drug.

Ocular prior and concomitant medications will be summarized using discrete summary statistics and presented separately for study eye and non-study eye. Non-ocular prior and concomitant medications will be similarly summarized but at the subject level. For the concomitant summaries, any data collected at and after rescue visits will not be used.

Subject concomitant medications will be presented in separate listings for ocular and non-ocular data. The listings will indicate if medications are prior and/or concomitant medications.

12 TREATMENT EXPOSURE AND NUMBER OF INJECTIONS

12.1 Study Injection Summary

The number of subjects receiving study injections in the Study Eye on Day 1 visit will be summarized with count and percentage by treatment group. Exposure data will be presented in listings.

13 EFFICACY ANALYSES

13.1 Primary Efficacy Endpoint

The study primary efficacy endpoint is the proportion of subject having a ≥ 15 -letter improvement (3-line gain) from baseline in best-corrected visual acuity (BCVA) at Month 6.

13.1.1 Primary Analysis

For the primary endpoint analysis, number and percentage of responders, with associated 2-sided exact (Clopper-Pearson) 95% confidence intervals (CIs), will be presented by treatment group. Proportion of responders will be compared between treatment groups using a two-sided Fisher's exact test. As stated in Section 7.10, subjects who received any rescue surgeries prior to Month 6 or drop out the study due to any reasons prior to Month 6 or missing data at Month 6 will be imputed as treatment failure (i.e. not improve by ≥ 15 letters).

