8. Have at least 42 days (6 weeks) since cataract surgery + PC-IOL, a minimum of 14 days (2 weeks) since yttrium-aluminum garnet (YAG) capsulotomy prior to screening visit.
9. BCVA between 65 Early Treatment of Diabetic Retinopathy Study (ETDRS) letters (i.e., 0.4 LogMAR or approximate 20/50 Snellen equivalent) and 5 ETDRS letters (i.e., 1.6 LogMAR or approximate 20/800 Snellen equivalent).
10. Have a CCT in the study eye of less than 1000 microns and greater than 575 microns, confirmed as per standard of care. If CCT is less than 575 microns, must have other documented clinical findings of corneal edema (i.e., Descemet's folds, bullous keratopathy, microcystic edema, or stromal haze).

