4 TRIAL DESIGN

4.1 Description of Trial

This is a multicenter, randomized, double-masked, parallel-arm, dose-ranging, Phase 1/2 study of AURN001 in subjects with corneal edema secondary to corneal endothelial dysfunction. The efficacy and safety of AURN001 will be assessed in a clinical trial setting in North America in adult subjects with corneal edema secondary to corneal endothelial dysfunction. Three doses of AURN001 compared with the 2 components of AURN001 separately (*neltependocel* and Y-27632) will be evaluated to assess the contribution of these 2 elements to the efficacy and safety of AURN001.

This trial will enroll approximately 100 subjects in the 5 treatment arms with approximately 20 subjects per arm. A randomized treatment sequence will be assigned. The sponsor will assess the actual enrollment in each arm on an on-going basis throughout the study to maintain a

randomization ratio of 1:1:1:1:1. The sponsor will make adjustments to the randomized treatment sequence and the number of subjects to be treated in each cohort as needed.

The treatment arms are as follows:

[figure not shown]
Table 1 Treatment Assignment Paradigm

Arm	No. of Subjects	Neltependocel Dose	Y-27632 Dose	Endothelial Polishing?
1	20	1.0×10^6	100 μ M	Yes
2	20	5.0×10^5	100 μ M	Yes
3	20	2.5×10^5	100 μ M	Yes
4	20	None	100 μ M	Yes
5	20	1.0×10^6	None	Yes

This study will have a screening period, a surgery/treatment day during which treatment will be administered, and a 12-month observation period. The primary efficacy analysis will be conducted at Month 6. The study will have up to 10 visits with one optional visit: the Screening Visit (Visit 1, -77 days to -7 days); Surgery/Treatment (Visit 2, Day 1); and Follow-up (Visits 3 through 10, Day 2, Week 1, Week 4, and Months 2 (optional), 3, 4.5, 6, 9, and 12, respectively). Unscheduled visits will be allowed, as deemed necessary by the investigator.

This study will be conducted per the schedule shown in Figure 1.

Figure 1 Study Schematic

Assessments can be found in the Schedule of Assessments in Appendix 1.

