4.3 Randomization and Masking

This study will be double-masked and will utilize a randomized treatment sequence model. A computer-generated encrypted read-only randomized treatment sequence schedule will be provided by a biostatistician. The randomized treatment sequence schedule will be managed by unmasked team members responsible for assessing enrollment in each arm to maintain a randomization ratio of 1:1:1:1:1.

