7.7 Adjustments for Multiplicity

7.8 Adjustment for Covariates

Change from baseline in BCVA and CCT at Month 6 will be analyzed using Analysis of covariance (ANCOVA) for the full analysis set. Baseline of BCVA and CCT will be used as covariate for the adjustment.

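### The 15-letter primary response is compared only by unadjusted Fisher tests; with eligible eyes spanning 5 to 65 letters and about 20 per arm, a supportive baseline-adjusted comparison should be prespecified beside them (minor).

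*SAP*

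**What the plan says.** **Primary comparison.** SAP 13.1.1 reports the responder percentage per arm with an exact interval, and then: "Proportion of responders will be compared between treatment groups using a two-sided" Fisher's exact test. Protocol 10.7 specifies the same test. Rescue, dropout or missing data at Month 6 counts as non-response. SAP 13.2 analyses 10-letter response at Month 6 in the same way.

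**Sensitivity analyses.** SAP 13.1.2 plans a completer analysis and a per-protocol analysis. Both repeat the unadjusted test. SAP 7.12 plans no subpopulations.

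**Where baseline is used.** SAP 7.8 and 13.2 apply ANCOVA to Month 6 change in BCVA and CCT: "Baseline of BCVA and CCT will be used as covariate for the adjustment".

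**Population and allocation.** Protocol 7.1, criterion 9, admits "BCVA between 65 Early Treatment of Diabetic Retinopathy Study (ETDRS) letters (i.e., 0.4 LogMAR or approximate 20/50 Snellen equivalent) and 5 ETDRS letters". SAP 4.1 plans "approximately 100 subjects in the 5 treatment arms with approximately 20 subjects per arm". SAP 4.3 describes a randomised sequence managed by unmasked staff "responsible for assessing enrollment in each arm to maintain a randomization ratio of 1:1:1:1:1"; it names no stratification factor. SAP 6.2 defines seven pairwise contrasts: three combination arms against each of two components, plus component against component.

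**Baseline tables.** SAP 10.2 summarises baseline BCVA by eye and then says: "In addition, screening BCVA will be summarized for study eye and non-study eye separately", as counts below 65 letters and at 65 or above.

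**Status.** SAP 7.3 to 7.6: not powered, descriptive, nominal p-values, no formal hypothesis.

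**The concern.** An eye entering at 65 letters must reach 80 to count as a responder; an eye entering at 30 must reach 45. If treated eyes tend towards a similar final acuity, which is plausible for a product expected to restore corneal clarity (Protocol 4.2), the better eyes at entry have less room to respond. A chance difference in baseline between two arms of about 20 would then pass into the observed response difference.

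The SAP accepts this logic for the secondary endpoint. It puts baseline in the model for Month 6 change in BCVA, then leaves it out of every analysis of the dichotomised version of the same measurement, without giving a reason.

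At stake is how well the trial's estimates can be read. They are meant to inform later designs (SAP 7.3) and to show what each component contributes (SAP 4.1). If an imbalance appears, an adjusted analysis chosen after the Month 6 unmasking would be post hoc.

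**Working it through.** The plan states no power or precision figure, so there is nothing to reproduce beyond 5 × 20 = 100. The documents give no SD for baseline BCVA and no relation between baseline and response. Everything below except the 5 to 65 range, the 15-letter threshold, about 20 per arm and the seven contrasts is an assumption.

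**Step 1. Size of chance imbalance.** For two arms of 20, the SE of the difference in mean baseline is SD × √(2/20) = 0.316 × SD. For a uniform baseline on 5 to 65, SD = 60/√12 = 17.32 and SE = 5.48. The 95% range is ±1.96 × 5.48 = ±10.7 letters, and the chance of 5 letters or more is P(|Z| ≥ 5/5.48) = 36%. The table repeats this for normal distributions with parameters 45/15 and 55/12, truncated to 5 to 65.

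**Step 2. Effect on response, model A.** With probability 0.7 the eye succeeds and ends at N(75, 10); otherwise it changes by N(0, 8). Expected response at baseline b is 0.7 × P(N(75,10) ≥ b + 15) + 0.3 × P(N(0,8) ≥ 15):

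- b = 30: 0.7 × 0.999 + 0.3 × 0.030 = 0.71
- b = 40: 0.7 × 0.977 + 0.009 = 0.69
- b = 50: 0.60
- b = 65: 0.7 × 0.309 + 0.009 = 0.23

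So the curve is flat over more than half the eligible range and falls steeply near the ceiling. Simulating pairs of arms of 20 gives slopes of the response difference on the baseline-mean difference of 0.61, 0.84 and 1.46 points per letter, in table order. The shift is 5 × slope. The share of variance is (slope × SE / SD of the response difference)²; for the uniform case, (0.61 × 5.48 / 15.3)² = 0.05.

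| Assumed baseline | SD | SE of mean difference | Chance of ≥5 letters, one contrast | At least one of seven | Shift per 5 letters (points) | SD of response difference (points) | Share of variance |
|---|---|---|---|---|---|---|---|
| Uniform 5–65 | 17.32 | 5.48 | 36% | 86% | 3 | 15.3 | 5% |
| Truncated normal 45/15 | 12.52 | 3.96 | 21% | 65% | 4 | 15.4 | 5% |
| Truncated normal 55/12 | 9.14 | 2.89 | 8% | 35% | 7 | 15.8 | 7% |

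The rows must be read across: the largest shift goes with the smallest chance of imbalance.

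**Step 3. Sensitivity to the assumed relation, model B.** Month 6 BCVA = constant + slope × (baseline − 45) + effect + N(0, 15). Baseline is uniform (SD 17.3) or skewed towards 65 (SD 12.3), with 2,500 runs per scenario.

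| Slope of final on baseline acuity | Shift per 5 letters (points) | Share of variance | SD of difference, unadjusted → adjusted, no true effect (uniform; skewed) |
|---|---|---|---|
| 0.2 | 7–9 | 19–34% | 15.4 → 12.7; 15.7 → 14.3 |
| 0.5 | 5–6 | 8–18% | 15.7 → 14.4; 15.5 → 14.9 |
| 0.8 | 2–3 | 2–3% | essentially unchanged |
| 1.0 | 0 | 0% | essentially unchanged |

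**Step 4. Test behaviour at 20 v 20.** Type I error in model B is 0.018–0.024 for Fisher and 0.051–0.067 for a baseline-adjusted likelihood-ratio test. By exact enumeration, Fisher's is 0.020 at 50% v 50% and 0.025 at 30% v 30%.

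With a 14-letter effect, Fisher rejects in 0.25–0.50 of runs and the adjusted test in 0.52–0.65. Much of that gap is Fisher's conservatism: at slope 1.0, where baseline is irrelevant, it is still 0.49–0.50 v 0.63–0.65. A like-for-like comparison of score tests with and without baseline under model A gives gains of 3 to 7 points (for example 0.52 to 0.55 and 0.65 to 0.72), with type I error of 0.047–0.062 for the adjusted score test.

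**The case against.** A reader might infer that baseline largely decides who can gain 15 letters. The documents do not support that. No eligible eye is arithmetically barred from response, since even a 65-letter eye needs only 80, and no baseline-response relation is given. In model A response barely changes up to 40 letters. In every scenario tried, ordinary binomial noise at 20 per arm accounts for more of the variance than baseline imbalance does.

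A reader might also infer that the primary comparison is biased or invalid. It is neither. Under randomisation the unadjusted difference is unbiased on average, and Fisher's test holds its level. The study calls itself descriptive, with nominal p-values, and an exact test with Clopper-Pearson intervals is defensible at this size. Replacing it with a model as the main comparison would be a trade-off, not a correction.

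Nor is baseline hidden. SAP 10.2, read with the summary conventions of SAP 6.1, gives the mean and SD of baseline BCVA, so a mean imbalance should be visible. The 65-letter cut is an extra table that also serves the non-study eye, which has no 65-letter limit. The ANCOVA of BCVA change already gives a baseline-adjusted comparison of the same measurement at the same visit.

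All of this stands. It does not remove the narrower point: nothing planned adjusts the binary endpoint. The ANCOVA also answers a different question, because it is on another scale and carries the last observation forward (SAP 7.10) where the primary analysis counts non-response.

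**Conclusion.** The point holds as a minor one. The 15- and 10-letter responses have no planned analysis that accounts for baseline BCVA, in a trial with a 60-letter eligible range, about 20 eyes per arm, no described stratification, and adjustment for the same baseline elsewhere in the SAP.

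Baseline is likely to be prognostic, but that is an inference. Under model A, the chance of a 5-letter imbalance in a given contrast and the resulting shift pair as 36% with 3 points, 21% with 4 points and 8% with 7 points, and imbalance explains about 5 to 7% of the variance of the difference. Model B widens that share to 0 to 34%. If final acuity tracked baseline letter for letter, adjustment would gain nothing.

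The consequence is some lost precision and a harder reading of any one observed contrast. There is no bias on average and no inflated error rate.

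**What to change.** Keep Fisher's exact test and the Clopper-Pearson intervals as the main analysis. Add to SAP 13.1.2, and to SAP 13.2 for 10-letter response, a prespecified supportive comparison on the Full Analysis Set:

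- the same non-responder imputation as the primary analysis;
- one model with five-level arm and continuous baseline BCVA, for example Firth-penalised logistic regression because cells may be small;
- a standardised risk difference with 95% CI for each of the seven SAP 6.2 contrasts.

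Minor addition: in SAP 10.2, tabulate study-eye BCVA in categories inside the eligible range, for example below 35, 35–54 and 55–65 letters. The 65-letter cut sits at the eligibility ceiling, so its upper group can hold only study eyes at exactly 65 letters or deviators.

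Cost: SAP wording and one model on data already collected. There is one more modelled estimate to explain beside the raw percentages. A term linear on the logit scale may fit imperfectly if response is flat and then falls, as in model A. The model-based test may be slightly liberal at 20 per arm (about 0.05 to 0.07 for the adjusted tests simulated; the Firth version was not itself simulated), so its p-value should be read as nominal.
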